The overall aim of this project is to investigate symptoms and quality of life of women with CF and UI, to document objective exam findings, and to perform a feasibility and tolerability study of common non-surgical management options for UI.¹⁵ We hypothesize that treatment adherence and tolerability of PFMT may be less than with reusable absorbent underwear or disposable intravaginal devise and that the majority of women with CF and UI will have objective SUI on exam. Through the application of well-established clinical and qualitative research methodologies, we will provide a rigorous investigation of UI in women with CF. We will take important steps towards improving the treatment of women with CF and UI, and inform the design of a larger, multi-center, randomized trial of treatment modalities.

Specific Aim 1 – Explore the experiences, attitudes, and knowledge of women with CF related to UI and potential treatment modalities. We will conduct individual, semi-structured interviews with women with CF with UI (n~20-30) to assess how UI impacts symptoms and quality of life, evaluate barriers they experience regarding access to care/treatment, assess knowledge of available treatment for UI, and determine factors that influence decision-making surrounding treatment options. Subjects will be recruited primarily through the Cystic Fibrosis Foundation's Community Voice registry.

Hypothesis: Women with CF will report UI symptoms, decreased quality of life, limited knowledge about potential treatments and preference towards treatment with low time commitments.

Specific Aim 2 – Evaluate the feasibility of a randomized controlled trial of non-surgical UI management options for women with CF. We will complete a pilot, feasibility study (n=30) to compare tolerability and symptom relief in women with CF and UI. Subjects will be recruited from both study sites after demonstrating bother from UI on standard questionnaires. They will undergo UI questionnaires and undergo a pelvic examination, non-invasive bladder scan ultrasound and a provocative stress test and then be randomized to either a disposable urethral support device (Impressa®), an absorbent product (Speax Reusable Underwear), or PFMT. Our primary outcome will be to determine the feasibility and tolerability of these options.

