Data Analysis: Transcripts will be analyzed through an iterative process of coding to identify themes. The principal investigator (PI) will develop an initial set of codes. Two coders will then independently review each transcript to apply the initial codebook and to identify additional codes using the NVivo qualitative analysis program. Using a consensus coding approach, after the first few transcripts are independently coded, the coders will meet to review their coding, discuss any discrepancies, and define any new codes; this will be repeated with subsequent transcripts using an iterative process until no new codes emerge. A senior co-investigator will be available to adjudicate any differences in interpretation and review the codebooks. The final coding scheme will be applied to all transcripts and the investigative team will identify central themes on the UI patient experience and treatment knowledge and preferences of women with CF. Representative quotations will be selected to illustrate themes identified.

[figure not shown]
Aim 2. – Evaluate the feasibility of a randomized controlled trial of non-surgical UI management options for women with CF.

Overview: Nonsurgical therapies for UI include 1) behavioral training (e.g., bladder training, to teach one to gradually hold urine for longer periods), 2) PFMT to improve function of the pelvic musculature, and 3) urethral support devices.³⁸ Additionally, newer reusable absorbent underwear have been used to decrease common issues with disposable pads such as vulvar irritation.¹² To inform a larger trial, we propose a randomized, feasibility trial of a disposable urethral support device (Impressa®), Speax™ Reusable Underwear, or PFMT. As there is no current data on objective physical exam findings in women with CF and UI and, thus, limited evidence supporting the belief that this is SUI, all subjects will have a non-invasive pelvic exam to complete a non-instrumented cough stress test (CST) with a full bladder.³⁹ Together, data on objective findings, baseline subjective bother on validated questionnaires, and improvement of symptoms will aid in power calculations for future, multi-center trial for treatment options in women with CF and UI.

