Description of Participants and Participating Study Sites: *Inclusion criteria:* 1) Female age 18 years or older 2) Diagnosis of CF 3) Self-reported UI (at least answer of “a little” on King’s Health Questionnaire – Question #2) 4) Fluent in spoken English 5) Ability to present for in-office exam and study procedures

Recruitment sites: Cystic Fibrosis Center (CF Center) at the University of Pittsburgh and the Johns Hopkins Cystic Fibrosis Center. These two sites have a current working relationship and also the capabilities for study procedures as discussed in facilities section. **Study Procedures:** Participants will be recruited at routine CF clinic visits and via telephone screening. Informed consent will be obtained before any study procedures are initiated. **Baseline visit.** Initial demographic questions and the King’s Health Questionnaire⁴⁰ will be completed at the baseline visit. Subjects will be given materials to complete a 2-day bladder diary.⁴¹ Participants will then have a pelvic exam for a visual urethral mobility examination⁴² and assessment of pelvic floor muscle strength.⁴³ This exam will be completed by the urogynecology faculty at either site. We will first perform a bladder scan ultrasound to assess current bladder volume and then a cough stress test (CST). (Figure 1) The exam will be performed in the supine/lithotomy position with ≥ 300 mL of fluid in the bladder. We will have the subject cough forcefully 1-4 times and the examiner will directly visualize the urethral meatus for the presence of leakage. Leakage of fluid from the urethral meatus coincident with/simultaneous to the cough(s) is considered a positive test consistent with SUI.

FIGURE 1

Randomized feasibility trial (Table 2). At the baseline visit, women will be randomized to either a disposable urethral support device (Impressa®), Speax™ Reusable Underwear, or PFMT. Randomization will be in a 1:1:1 allocation stratified by site. The disposable Impressa® urethral support is a tampon-like device that is available over the counter to help women with UI. Speax Reusable Underwear are similarly available for purchase online and are absorbent underwear for bladder leak protection. **Urethral support device cohort** - A week supply of the Impressa device will be provided and participants will be asked to complete a daily bladder

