diary for a total of 7 days. Reusable absorbent pad cohort – Two pairs of Speax underwear will be provided and subjects will complete a similar daily UI diary for 7 days. PFMT cohort - Experienced pelvic health physical therapists (at both University of Pittsburgh and at Johns Hopkins University) will complete two visits one week apart. We will develop a standardized pelvic floor exercise intervention based on previous RCT for PFMT in women with MUI.⁴⁴ The intervention will comprise: 1) Bladder training and delayed voiding techniques 2) Urgency suppression 3) SUI strategies (e.g., 'knack') and 4) PFM training for those agreeable to internal exams.⁴⁵ We were aware of the potential challenges for standardization of this type of intervention and ensuring consistency across multiple sites. We will limit the involvement to one experienced PT at each site and create a standardized protocol guided by both patient consultants, previous evidence, and expertise of [name], RT. Subjects will not be blinded to their group assignment given the nature of the differences in management options. At the end of the treatment assignment all subjects will repeat the KHQ and a patient global impression of improvement (PGI-I). The PGI-I is a validated one question measure rating their urinary tract condition now, as compared with how it was prior to before beginning treatment on a scale from 1 (Very much better) to 7 (Very much worse).⁴⁶

Given the opportunity to gather acceptability on these options for a sensitive issue, subjects will be offered an option to further participate in one alternate therapy of their choosing. If they select this option we will organize an additional week of therapy and have them complete another PGI-I at the end of therapy.

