Acceptability and Feasibility assessment: Urethral support device cohort and Reusable absorbent pad cohort: Feasibility will be evaluated through assessment of use and product performance. Logs regarding utilization of assigned product will be completed daily. Patient treatment preference will be assessed after completion of both therapies utilizing the product performance questionnaire (PPQ).⁴⁷ The PPQ is a 17-item product questionnaire that consists of product questions that are specific to incontinence products and includes questions about overall impression of product, ability to hold urine, ability to prevent odor, fit, discreteness, comfort when wet and dry, and ability to keep skin dry.⁴⁷ PFMT cohort: Feasibility will be evaluated through assessment of adherence and self-reported success with ability to perform exercises. Adherence to intervention sessions will be documented by physical therapist using attendance logs. Adherence to home practice will be documented by participants in home logs that included the dates and times of practice. At the end of each physical therapy visit, participants will be asked to rate their confidence in performing the PFMT exercises featured in their program (extremely, very, moderately, somewhat, and not at all confident).

At the end of the cohort, all participants will be asked to indicate how easy it would be to continue practicing their assignment intervention (extremely, very, moderately, somewhat, and not at all easy).⁴⁸ All subjects will complete a Benefit, Satisfaction, and Willingness to Continue (BSW) questionnaire.⁴⁹ We will consider therapy feasible (as measured by 80% adherence to treatment assignment over 7 days) and tolerable (as measured by patient report via questionnaire). By allowing subjects to choose another one of the arms after their randomization this will give us further, important information about feasibility and patient preference for a larger trial.

Table 2: Study Flow

	Pre-baseline visit	Baseline Visit (in-person)	Randomized Trial Period							One week Cross-Over Period (optional)	End of Study
			D1	D2	D3	D4	D5	D6	D7		
Informed Consent	x	x									
KHQ		x									
Bladder diary	x		x	x	x	x	x	x	x		
Cough Stress test	x										
Randomization	x										
PGI-I									x		x
BSW								x			x
Cohort Specific Measures											
Urethral support device Cohort										x	
Reusable Underwear Cohort										x	
Utilization log			x	x	x	x	x	x	x		
PPQ			x	x	x	x	x	x	x		

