Physical Therapy Cohort											
Physical Therapy Visit			x						x		

Attendance Log			x				x		
Confidence scale			x				x		

KHQ, King's Health Questionnaire; PGI-I, Patient Global Impression Improvement – Incontinence; PFMT, pelvic floor muscle therapy; PPQ, product performance questionnaire; BSW, Benefit, Satisfaction, and Willingness to Continue questionnaire

Data analysis: Descriptive statistics will summarize feasibility survey measures and use log data with sample means and standard deviations calculated for continuous variables and sample proportions for categorical variables with 95% confidence intervals. Due to the pilot nature of this trial, our analytic strategy centers on calculation of point estimates and 95% confidence intervals of our feasibility measures as primary outcomes, rather than hypothesis testing. We will compare initial subjective scores of UI to objective measures utilizing correlation coefficients. To explore preliminary efficacy, PGI-I score will be compared between groups utilizing ANOVA and post-hoc testing. Paired t-test will be used to examine if there is statistically significant difference in the average KHQ scores between arms. The mean PPQ scores will be compared between the Impressa® urethral support and Speax™ underwear and mean BSW score will be compared between all groups. For our randomized trial, we will recruit a total of 30 patients in order to have 80% power to detect at least a 10 point difference in total KHQ score with a significance level of 0.05 and assuming upwards of a 20% attrition rate for the study. Again, the feasibility trial is primarily designed to provide data to utilize for power calculations in future study designs.

F. Limitations and Potential Pitfalls:

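### A paired t-test is specified for comparing KHQ between three unmatched arms, so the exploratory KHQ comparison has no usable between-arm method

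*Combined protocol and SAP*

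**What the plan says.** The test is set in section E, Aim 2, Data analysis: "Paired t-test will be used to examine if there is statistically significant difference in the average KHQ scores between arms". The same paragraph compares PGI-I between groups by ANOVA with post-hoc tests. It makes estimates of the feasibility measures, with 95% confidence intervals, the primary outcomes in preference to hypothesis tests. It justifies 30 patients by 80% power for a 10-point difference in total KHQ at a 0.05 significance level, allowing for up to 20% attrition. No SD is given, nor whether the difference is between arms or over time.

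The rest of Aim 2 fixes the data structure:

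- Allocation: "Randomization will be in a 1:1:1 allocation stratified by site".
- First KHQ (Baseline visit): the questionnaire "will be completed at the baseline visit".
- Second KHQ (Study Procedures): "At the end of the treatment assignment all subjects will repeat the KHQ".
- Optional second therapy, chosen by the woman: "we will organize an additional week of therapy and have them complete another PGI-I at the end of therapy". KHQ is not named here.

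Specific Aim 2 describes the pilot as intended "to compare tolerability and symptom relief in women with CF and UI". The Aim 2 Overview adds that data on "improvement of symptoms will aid in power calculations for future, multi-center trial". In "Table 2: Study Flow", as extracted, KHQ is marked only at the baseline visit. That may be an artefact of extraction.

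**The concern.** A paired t-test needs two linked measurements on each unit. Randomisation within site strata does not link a woman in one arm to a woman in another, so the test has no defined pairs, and a single t-test cannot compare three arms. If the sentence was meant as a baseline to end-of-assignment test, that test is valid for change within an arm and serves the aim of describing improvement, but it does not give the between-arm comparison that the sentence names. An analyst cannot tell from the text whether the test or the comparison is the part to change.

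Two things are at stake. First, without a between-arm method, three within-arm p-values may be read as a comparison. Second, KHQ is the only endpoint in the sample size statement, so a reader may take the 80% power to apply between arms.

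**Working it through.** **1. Is there any KHQ pairing across arms?** Each woman gives KHQ at baseline and at the end of her assigned treatment, both under one allocation. Site stratification is not matching. The optional week is self-chosen and adds only PGI-I. No woman is planned to give KHQ under two options, so the only pairing is over time within a woman.

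**2. Can the plan's 30 be reproduced?** Only the attrition step can: 30 × (1 − 0.20) = 24 completers, or 8 per arm. Without an SD or a stated contrast the power claim cannot be checked. Solving for the largest SD that gives 80% power for 10 points (noncentral t, two-sided 0.05):

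- pre/post test pooling all 24 women: SD of change up to about 16.7
- 8 versus 8 between two arms: SD up to about 6.6

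At SD 16.7, two arms of 8 have noncentrality 10 / (16.7 × √(2/8)) = 1.20. Power is 20% with 14 df and 21% with the 21 residual df of a three-arm model.

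**3. Literal pairing of two arms of 8, in arbitrary order.** For a true difference of 1.5 SD the noncentrality is 1.5 / √(2/8) = 3.0 for both tests, but the paired test has 7 df and the independent test 14. Power is 73% against 80%. In simulation (100,000 replicates) type I error was 0.051 and 0.050. The cost is modest power, not false positives.

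**4. Within-arm tests used in place of a comparison.** Assume a true improvement of 10 points in all three arms and n women per arm. Within-arm power q comes from the noncentral t with n − 1 df and noncentrality 10 / (SD/√n). The chance that some arms are significant and others are not is 1 − q³ − (1 − q)³. For example, at n = 8 and SD 10 the noncentrality is 10 / (10/√8) = 2.83 and q = 0.681, so the chance is 1 − 0.316 − 0.032 = 0.652.

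| SD of change (assumed) | q, n = 8 | Mixed result, n = 8 |
|---|---|---|
| 5 | 0.998 | 1% |
| 6 | 0.980 | 6% |
| 7 | 0.931 | 19% |
| 8 | 0.856 | 37% |
| 8.65 | 0.800 | 48% |
| 10 | 0.681 | 65% |
| 12 | 0.528 | 75% |
| 16.7 | 0.311 | 64% |
| 25 | 0.166 | 41% |
| 40 | 0.094 | 26% |

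The chance is below 5% for SDs under about 5.9 and above 50% only for SDs of about 8.8 to 21. With no attrition (n = 10) it is under 1% at SD 5, 47% at SD 10, 68% at SD 12 and 49% at SD 25.

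**5. The same scenario with a three-arm method.** Three arms of 8 were simulated with an assumed baseline to follow-up correlation of 0.6, at SDs of change of 5, 8.65, 12 and 25. ANOVA of change rejected in 0.049, 0.048, 0.050 and 0.049 of 20,000 replicates. ANCOVA with baseline and site rejected in 0.054, 0.048, 0.051 and 0.048 of 5,000. Both hold about 5% whatever the SD.

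**The case against.** The strongest reply is that the sentence is a slip of wording with little consequence. It follows directly on the ANOVA and post-hoc tests for PGI-I, so 'paired' may stand for 'pairwise'; independent t-tests between pairs of arms would then be a between-arm method. Symptom relief is in any case compared across all arms through PGI-I, and BSW is compared too. The mixed-significance figures depend on a use of within-arm tests that the plan does not describe, on equal 10-point gains and on an assumed SD. A mixed pattern of p-values is also not the same event as a declared difference by ANOVA. Feasibility is primary, and KHQ means, SDs and correlations can be estimated whichever test is run.

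Much of this stands. The figures in step 4 describe a risk, not a stated analysis; the only figures tied to the literal sentence are those in step 3, and they are mild. The loss of the KHQ comparison does not leave symptom relief uncompared. The 'pairwise' reading does not rescue the text, however: it requires the word to be changed, and it still gives KHQ no three-group method like the one PGI-I has. On every reading the sentence has to be rewritten before it can be followed.

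**Conclusion.** The concern holds. As written the KHQ test is undefined between arms, and in its only workable form it compares no arms. This follows from the design and needs no outside figure. It should be fixed, but its reach is limited: the outcome is exploratory, the primary feasibility estimates are unaffected, and each test taken singly keeps about 5% type I error.

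The size of the risk depends on assumptions: 8 evaluable women per arm, the same true 10-point gain in each, and an SD of change that the documents do not give. It is negligible for SDs below about 5.9 and exceeds an even chance only between about 8.8 and 21. The 20% between-arm power is likewise illustrative, because the SD of 16.7 was obtained by solving for a pooled pre/post test that the plan does not state.

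**What to change.** Replace the sentence with wording such as: *End-of-assignment KHQ will be compared between the three arms by ANCOVA with arm as a factor and baseline KHQ and site as covariates, reporting pairwise mean differences with 95% CIs as exploratory estimates. Pre/post change within each arm will be summarised descriptively.* ANOVA of KHQ change, in line with the PGI-I method, is an acceptable alternative.

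Two related edits are needed. Check that Table 2 shows KHQ repeated at the end of assignment. In the power sentence, state the contrast and SD to which the 80% refers; if it was a pooled pre/post test, say that it does not apply between arms.

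The cost is two sentences and one table check, with no new data, visits or patients. The Timeline still has the Aim 2 protocol to be finalised. With 24 women, ANOVA of change has 24 − 3 = 21 residual df and ANCOVA with two covariates has 19. The power statement may become less favourable once its contrast is named.

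### The 80% power claim for a 10-point KHQ difference names no SD and no comparison, and the test attached to it cannot compare independent arms

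*Combined protocol and SAP*

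**What the plan says.** All of this is in the Combined protocol and SAP, section E, Aim 2.

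- **Sample size (Data analysis).** The trial recruits "30 patients in order to have 80% power to detect at least a 10 point difference in total KHQ score". Testing is at the 5% level, and the allowance for loss to follow-up is about one fifth of the women. The sentence is introduced as applying to the randomized trial. It gives no SD, source or sidedness, and does not say whether the 10 points are between arms or before to after.
- **KHQ analysis (same paragraph).** "Paired t-test will be used to examine if there is statistically significant difference in the average KHQ scores between arms".
- **Design (Randomized feasibility trial).** "Randomization will be in a 1:1:1 allocation stratified by site", so 10 women per arm are recruited. The text has KHQ completed at baseline and repeated at the end of the assigned treatment.
- **Status of the comparison.** The paragraph makes feasibility estimates with 95% confidence intervals primary, in place of hypothesis testing, and introduces its efficacy comparisons as exploratory. Section F names the small Aim 2 sample as the main limitation.

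**The concern.** A power statement needs a comparison, an effect, a variability, a significance level and a test. This one lacks the comparison and the variability, and the KHQ test in the same paragraph contradicts itself. A paired t-test works on each woman's own before and after scores. It cannot test a difference between groups made up of different women.

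The missing comparison matters because the two plausible readings differ greatly. A before-after test can pool all 24 completers, whereas a comparison of two arms has 8 against 8. The same sample and the same 10 points cannot give both tests 80% power at one SD.

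This is the only quantitative justification for the Aim 2 sample size (Aim 1 has its own, qualitative one). The trial is also meant to supply figures for powering a later definitive study. A reader who takes the 80% to apply between arms could read far too much into a null KHQ comparison.

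**Working it through.** **Inputs from the documents:** 30 recruited; 1:1:1 allocation; attrition taken as 20%; 10 points; alpha 0.05; power 80%.

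**Assumptions:** two-sided testing, equal attrition across arms, normal theory. No SD is stated, so 30 cannot be computed forward. Instead I solve for the SD that each reading needs.

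**Completers.** 30 × (1 − 0.20) = 24, and 24 / 3 = 8 per arm.

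**Power formula.** Power = P(|T| > t_crit), where T is noncentral t with parameter λ.
- Two independent arms, n each: df = 2n − 2, λ = 10 / (SD × √(2/n)).
- Paired, n women: df = n − 1, λ = 10 × √n / SD of change.

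**Reproducing the plan's 30**

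| Reading | Detectable effect at 80% power | SD needed for 10 points |
|---|---|---|
| Two arms, 8 v 8 | 1.507 SD | 10 / 1.507 = 6.6 |
| Two arms, 10 v 10, no attrition | 1.325 SD | 10 / 1.325 = 7.5 |
| Paired within one arm, n = 8 | 1.156 SD | 10 / 1.156 = 8.7 |
| Paired, pooled over arms, n = 24 | 0.597 SD | 10 / 0.597 = 16.7 |

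A normal-approximation check, using 1.960 + 0.842 = 2.802:
- 8 v 8: 2.802 × √(2/8) = 1.401 SD, so SD 7.1.
- Pooled paired: 2.802 / √24 = 0.572 SD, so SD 17.5.

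One-sided testing moves the exact values to 7.6 (8 v 8) and 19.1 (pooled).

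The figure of 30 therefore reproduces under more than one reading. At an SD of 6.5 a two-arm test needs 8 per arm: 24 completers, and 24 / 0.8 = 30 recruited. At an SD of change of 16.7 a pooled paired test needs 24 completers, and again 30 recruited.

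**Between-arm power for a true 10-point difference, 8 v 8, two-sided 5%** (every SD is an assumption)

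| SD | 6.5 | 7 | 8 | 10 | 12 | 15 | 16.7 | 20 | 25 | 30 |
|---|---|---|---|---|---|---|---|---|---|---|
| Power | 82% | 76% | 64% | 46% | 34% | 24% | 20% | 15% | 12% | 10% |

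**If the pooled before-after reading was meant.** At SD 16.7 the standard error of the difference between two arms in mean change is 16.7 × √(2/8) = 8.35. Then λ = 10 / 8.35 = 1.20, and power is 20% (24% with 10 per arm). The 95% confidence interval half-width is 2.145 × 8.35 = 17.9 points, wider than the 10-point target. Reaching 80% for one pair at that SD would take 45 completers per arm.

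The 20% refers to change scores. If final scores alone were compared, power would run from 35% to 11% as the before-after correlation goes from 0 to 0.8. With baseline adjustment it would run from 35% to 22%.

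**The case against.** The strongest reply is that no calculation in the plan has been shown to be wrong. With no SD stated, 30 is right under any reading for some SD, and nothing in the documents excludes one near 6.6. The power sentence does not itself say between arms, and a sentence on other outcomes separates it from the KHQ test. KHQ is measured before and after treatment, so a before-after intent is plausible. On that reading 80% is reached if the SD of change is 16.7 or less, and the fault is a mislabelled test. KHQ efficacy is also exploratory, and the plan openly defers efficacy to a later trial.

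Most of this stands, and it limits what can be claimed. A reader might infer that 30 can only come from a pooled before-after test, or that the true between-arm power is 20%. The documents support neither. A two-arm test also returns 30 at an SD near 6.6, and the 16.7 behind the 20% is back-solved from one reading rather than stated in the plan.

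The reply does not rescue the text. The between-arm reading needs a difference of 1.5 SD, which is nowhere justified, and conflicts with the paired test named. The before-after reading conflicts with that same sentence's reference to arms. The pilot status does not settle it either, because the paragraph still plans a significance test between arms and still rests 30 on 80% power.

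**Conclusion.** The point holds as a fault in the text, of moderate severity because the outcome is exploratory. Two parts need no SD. The power claim cannot be verified, since comparison and variability are missing, and a paired t-test is the wrong tool for a difference between independent arms. A third follows from the sample size, two-sided testing and 20% attrition spread evenly: with 8 completers per arm, 80% pairwise power needs about 1.5 SD, so 10 points requires an SD of about 6.6 or less (7.5 with no attrition).

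The 20% between-arm power is conditional. It applies if the figure came from a pooled paired test with an SD of change near 16.7 and change scores are then compared between arms. It should not be reported as the trial's actual power. The feasibility objective is not affected.

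**What to change.** 1. Restate the power sentence so that it names the comparison, the sidedness, the SD and the source of that SD. The value of 16.7 derived here should not be entered as if it were sourced.
2. Add a sentence such as: with about 8 completers per arm, the between-arm KHQ difference detectable with 80% power at a two-sided 5% level is about 1.5 SD.
3. If no SD can be supported, remove the 80% claim and justify 30 by the expected width of the 95% confidence intervals for the feasibility measures, which are the stated primary outcomes.
4. Use the paired t-test only for before-after change. Report between-arm KHQ differences as estimates with 95% confidence intervals from an independent-groups analysis of change, with no significance claim.

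The cost is a few sentences of protocol text and no extra patients. The sponsor gives up a more favourable stated figure and one exploratory significance test.
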